## 7.6 RANDOMISATION

The trial will be performed as a double-blind design with respect to placebo and empagliflozin. Patients will be randomised to the trial treatments in a 1:1 ratio.

No stratification will be performed in this trial.

Patients will be randomised in blocks to double-blind treatment via an IRT system.

Approximately equal numbers of patients will be randomised to each treatment group.

BI will arrange for the randomisation and the packaging and labelling of trial medication. The randomisation list will be generated using a validated system, which involves a pseudo-random number generator so that the resulting treatment will be both reproducible and non-predictable. The block size will be documented in the Clinical Trial Report. Access to the codes will be controlled and documented.

## 7.7 DETERMINATION OF SAMPLE SIZE

In clinical studies, 30-50 meters have been variably reported as a meaningful distance achieved as a result of therapy [\[R17-1227\]](#).

The SD of 72 m is assumed for sample size considerations of this trial [\[R17-1225\]](#). The risk of observing a higher SD in this trial will be mitigated by using duplicate measurements of 6MWT at baseline, Week 6 and Week 12 [\[R17-2791\]](#). For none-missing values a normal distribution for change from baseline in distance walked in 6 minutes is assumed in all below sample size estimations.

The trial is designed to achieve a power of 90% for a two sided test at level  $\alpha = 0.05$  to detect a difference between empagliflozin and placebo.

Using a normal distribution to calculate the probability that an observation X in Empagliflozin group will be less than an observation Y in the control group under the alternative, the following table presents the number of required evaluable patients for different assumed means of absolute difference in distance walked within 6 minutes as obtained by using the Wilcoxon sample size estimation procedure from commercial software nQuery Advisor® 7.0 statistical package by Statistical Solutions Ltd.

Table 7.7: 1 Sample size calculation

True treatment difference in distance walked in 6 minutes	SD	P(X<Y)	Required number of patients per group
30 m	72 m	0.384	131
40 m	72 m	0.347	76
50 m	72 m	0.312	50

A true treatment difference of 30 m is used as a conservative measure for sample size calculation to ensure that the study could detect the lowest effect size reported to be meaningful.

Therefore, a total of 131 evaluable patients per group are needed in order show a significant result for a two-sided test at level  $\alpha = 0.05$  with a power of 90% not considering missing data.

To assess the impact of missing data a simulation with 100000 iterations was performed. A normal distribution for 6MWT distance was assumed and a total of 5%, 8% and 10% patients imputed to worst case as outlined in [section 7.5](#) in each treatment group were investigated. The results are summarized in [Table 7.7: 2](#).

Table 7.7: 2 Simulation of imputation rules

N per group	Simulated true treatment difference for non-missing data [mean $\pm$ SD]	Percentage of missing data imputed to worst case	Power
150	30 $\pm$ 72	5%	90%
150	30 $\pm$ 72	8%	87%
150	30 $\pm$ 72	10%	85%

Therefore, a total of 150 patients per treatment group will allow for a drop-out and imputation of about 5% of the patients in order to show a significant result for a two-sided test at level  $\alpha = 0.05$  with a power of 90%. With a drop-out rate of 10%, a total of 150 patients per treatment group would still yield a power of 85%.

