### 7.7.1 Power estimation for key secondary endpoints

#### KCCQ

For power estimation of the KCCQ-TSS a treatment difference of 5 points is assumed. In patients with heart failure previous studies have reported a standard deviation of the KCCQ TSS between 13 in the CONFIRM-HF trial and 19-21 in the FAIR-HF trial [[R17-1226](#), [R17-3097](#)].

Using a normal distribution to calculate the probability that an observation X in Empagliflozin group will be less than an observation Y in the control group under the alternative, a sample size of 150 per treatment group will result in approximately 55% to 90% power to detect a 5 point difference between treatment groups at an alpha-level of 5% using a Wilcoxon test, if all questionnaires are available at the end of the trial ([see Table 7.7.1: 1](#)).

Due to the Hochberg procedure, if CHQ dyspnea is not significant, an alpha-level of 2.5% will become applicable. [Table 7.7.1:1](#) therefore additionally shows an alpha-level of 2.5 %.

Table 7.7.1: 1 – Power Estimation for KCCQ-TSS

SD	P(X<Y)	Power for $\alpha = 5\%$	Power for $\alpha = 2.5\%$
13	0.393	89%	83%
15	0.407	79%	71%
17	0.418	69%	59%
20	0.430	55%	44%

While every effort will be made to collect the questionnaire for randomized patients regardless of being on or off treatment, about 5% missing questionnaires may be assumed and are considered for power evaluation in analogy with the primary endpoint.

Results of a simulation of the power with 100000 iterations to detect a 5 point difference between treatment groups in a Wilcoxon test with imputation rules analogously to the primary endpoint, assuming 5% missing questionnaires at week 12 in each treatment arm, a normal distribution for non-missing scores, and alpha of 5% is summarized in the [Table 7.7.1: 2](#) below.

Table 7.7.1: 2 – Simulation of Imputation Rules for KCCQ-TSS

SD	Power for $\alpha = 5\%$	Power for $\alpha = 2.5\%$
13	85%	76%
15	73%	61%
17	61%	49%
20	47%	35%

Overall power is reasonable to evaluate superiority of empagliflozin versus placebo assuming a treatment effect of 5 points and a standard deviation that does not exceed 15 points.

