### CHQ

For power estimation of the CHQ dyspnea a treatment difference of 0.5 points is assumed [[R99-1220](#)]. CHQ and CRQ (an instrument almost identical to CHQ used in respiratory disease) are reported as performing similarly [[R99-1220](#)]. A standard deviation of the change

from baseline of the standardized CRQ dyspnea score of 1.15 has been reported [[R05-1404](#)]. Similar data were also reported for CHQ [[R17-2917](#)]. Therefore, for power estimation, a standard deviation of 1 to 1.4 is assumed.

Using a normal distribution to calculate the probability that an observation X in Empagliflozin group will be less than an observation Y in the control group under the alternative, a sample size of 150 per treatment group will result in approximately 84% to 98% power per score to detect a 0.5 point difference between treatment groups at an alpha-level of 5% using a Wilcoxon test, if all questionnaires are available at the end of the trial (see [Table 7.7.1:3](#)).

Due to the Hochberg procedure, if KCCQ-TSS is not significant, an alpha-level of 2.5% will become applicable. [Table 7.7.1: 3](#) therefore additionally shows an alpha-level of 2.5 %.

Table 7.7.1: 3 – Power Estimation for CHQ-SAS

SD	P(X<Y)	Power for $\alpha = 5\%$	Power for $\alpha = 2.5\%$
1	0.362	98%	97%
1.2	0.384	93%	89%
1.4	0.400	84%	77%

While every effort will be made to collect the questionnaire for randomized patients regardless of being on or off treatment, about 5% missing questionnaires may be assumed and are considered for power evaluation in analogy with the primary endpoint.

Results of a simulation of the power with 100000 iterations to detect a 0.5 point difference between treatment groups in a Wilcoxon test with above imputation rules, assuming 5% missing questionnaires at week 12 in each treatment arm, a normal distribution for non-missing scores, alpha of 5% is summarized in the [Table 7.7.1:4](#) below.

Table 7.7.1: 4 – Simulation of Imputation Rules for CHQ-SAS

SD	Power for $\alpha = 5\%$	Power for $\alpha = 2.5\%$
1	98%	95%
1.2	90%	83%
1.4	79%	69%

Overall a power of approximately 70% or higher is expected to detect a difference of 0.5 for each score given the planned sample size of 150 patients per treatment group.

Calculations were performed using nQuery Advisor® 7.0 statistical package by Statistical Solutions Ltd and simulation was performed using R version 3.3.2 by The R Foundation for Statistical Computing.

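### The stated power of 90%, 87% and 85% at 5%, 8% and 10% drop-out assumes that both arms lose the same number of patients; with random drop-out at equal rates it is about 88%, 84% and 81%

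*Protocol*

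**What the plan says.** Protocol Section 7.7 sizes the trial for the Wilcoxon test on change in 6MWT distance: "The trial is designed to achieve a power of 90% for a two sided test at level" 0.05, with a 30 m difference and an SD of 72 m. To allow for missing data it reports a simulation with "a total of 5%, 8% and 10% patients imputed to worst case as outlined in" Section 7.5, the same percentage being applied to each arm. Table 7.7:2 gives 90%, 87% and 85% power with 150 per group.

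The text after the table turns these into statements about a drop-out rate. The planned number "will allow for a drop-out and imputation of about 5% of the patients in order to show a significant result" with 90% power. Then: "With a drop-out rate of 10%, a total of 150 patients per treatment group would still yield a power of 85" per cent. Neither sentence says that the arms are taken to lose equal numbers.

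Section 7.7.1 uses the same approach for the key secondary endpoints: KCCQ-TSS "assuming 5% missing questionnaires at week 12 in each treatment arm" (Table 7.7.1:2), and CHQ-SAS dyspnea "with above imputation rules, assuming 5% missing questionnaires at week 12 in each treatment arm" (Table 7.7.1:4).

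**The concern.** A drop-out rate is a chance per patient. Block randomisation (Section 7.6) balances the numbers randomised, not the numbers lost. In many analyses a small imbalance in losses hardly matters, but here every missing patient is placed below every measured value, so the difference in missing counts is itself part of the test statistic. A simulation that holds the two counts equal removes that source of variance and reports too much power.

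The 10% sentence is the protocol's reassurance should drop-out exceed the plan. A reader relying on it would accept a 15% risk of missing a true 30 m effect when the risk is nearer 19%.

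**Working it through.** **Inputs (Protocol).** Difference 30 m ("A true treatment difference of 30 m is used as a conservative measure for sample size calculation"); SD 72 m ("The SD of 72 m is assumed for sample size considerations of this trial"); normal distribution for measured values; two-sided alpha 0.05; 150 per arm (Section 7.7). Wilcoxon test by normal approximation on all randomised patients (Section 7.3.1). Missing values ranked below all measured values (Section 7.5). The documents give no drop-out model. The random case below assumes independent drop-out, the same rate in both arms, and no relation to outcome.

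**1. The plan's own figures.** P(X<Y) = Φ(−30/(72√2)) = 0.384. Then n = (1.960+1.282)²/[6(0.38414−0.5)²] = 130.5, so 131 per group, as stated. With 150 per arm and nothing missing, simulated power is 94.0%.

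**2. Simulated power, 100,000 iterations per cell.**

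| Missing | Stated | Equal fixed counts (8, 12, 15 per arm) | Binomial(150, rate) in each arm |
|---|---|---|---|
| 5% | 90% | 90.1% | 88.4% |
| 8% | 87% | 87.3% | 84.1% |
| 10% | 85% | 84.9% | 80.8% |

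Equal fixed counts reproduce Table 7.7:2; random counts do not. Treating imputed values as tied or distinct, applying a continuity correction, or fixing only the pooled missing total left the random results at 88.3–88.6%, 84.0–84.3% and 80.7–80.8%. Random drop-out gives 90.4% power at 3.5% missing and 89.7% at 4%.

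**3. Hand check at 10%.** Let a and b be the missing fractions on empagliflozin and placebo. The chance that an empagliflozin patient ranks above a placebo patient, ties counted as half, is

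θ = (1−a)(1−b)·0.6159 + (1−a)b + ab/2.

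The null SE is √[301/(12·150²)] = 0.0334.

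- 15 v 15 missing: θ = 0.4988 + 0.0900 + 0.0050 = 0.5938, expected z = 0.0938/0.0334 = 2.81.
- 17 v 13 missing: θ = 0.5805, expected z = 2.41. Each patient of difference therefore moves z by (2.81−2.41)/4 = 0.10.
- SD of z with counts fixed: for m = 135 measured per arm, Var = [p(1−p)+2(m−1)(p₁−p²)]/m² with p = 0.6159 and p₁ = 0.4570 (one empagliflozin value exceeding two placebo values) gives 0.001156, SD 0.0340. Scaled by (135/150)² and divided by 0.0334, this is 0.825.
- SD of the difference in missing counts: √(2·150·0.1·0.9) = 5.20, which adds 5.20 × 0.10 = 0.52 on the z scale.

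Power with fixed counts: Φ((2.81−1.96)/0.825) = 84.9%. Power with random counts: total SD √(0.825²+0.52²) = 0.975, so Φ(0.85/0.975), about 81%. The closed form gives 90.5% v 88.6% at 5% and 87.4% v 84.2% at 8%.

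**4. Size and frequency of imbalance.** The SD of the difference in counts is 3.8, 4.7 and 5.2 patients at 5%, 8% and 10%. A difference of 4 or more occurs in 35%, 45% and 50% of trials. Power at 10%, 30 missing in total, 50,000 iterations:

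| Split | More missing on placebo | More missing on empagliflozin | Average |
|---|---|---|---|
| 14/16 | 89.6% | 78.6% | 84.1% |
| 13/17 | 93.4% | 70.9% | 82.2% |
| 12/18 | 96.0% | 62.3% | 79.1% |
| 10/20 | 98.6% | 43.0% | 70.8% |

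**5. Key secondary endpoints, 5% missing, equal fixed v random counts.**

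| Endpoint, SD | Alpha 5% | Alpha 2.5% |
|---|---|---|
| KCCQ 13 | 84.8 v 83.1 | 76.4 v 75.0 |
| KCCQ 15 | 73.0 v 71.7 | 61.8 v 61.4 |
| KCCQ 17 | 60.8 v 60.9 | 48.6 v 49.6 |
| KCCQ 20 | 46.9 v 47.7 | 35.1 v 36.6 |
| CHQ 1 | 97.5 v 96.7 | 95.0 v 93.9 |
| CHQ 1.2 | 90.1 v 88.4 | 83.5 v 82.0 |
| CHQ 1.4 | 78.8 v 77.4 | 68.7 v 68.0 |

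Where power is below about one half, extra variance raises it slightly, which is why KCCQ at SD 20 goes up.

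**The case against.** Table 7.7:2 contains no arithmetic error. It is right for equal missing counts, it says that the percentage was applied per arm, and the sentences after it plainly draw on it. Fixing the missing fraction in each arm is a familiar planning simplification. The random-count figures replace one assumption with another, and they depend heavily on equal true rates: at 8% on empagliflozin and 12% on placebo power would be 93.2%, and with the rates reversed 60.1%. At the planned drop-out of about 5% the gap is under 2 points, and no conclusion about the key secondary endpoints changes.

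Most of this stands. The table is correct on its own condition, the 5% gap is small, imbalance can raise power as well as lower it, and any figure needs a stated drop-out model. Even a two-patient difference moves power by 5 to 6 points in one direction or the other, so near-equality preserves the stated figure only on average over the two directions.

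The objection does not rescue the sentences about a drop-out rate. Equal percentages are not equal realised counts, and a reader cannot tell from the text that the counts were held equal. Independent loss at a common rate is the ordinary meaning of the term, and under it the 8% and 10% figures are too high by well more than simulation error, which is about 0.2 points.

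**Conclusion.** The concern holds. The stated 90%, 87% and 85% are conditional on equal missing counts. Presented as power at a given drop-out rate, they are too high by about 1.5 points at 5%, 3 points at 8% and 4 points at 10%. These gaps rest on 150 per arm, 30 m, SD 72 m, worst-rank imputation, and independent drop-out at one rate in both arms unrelated to outcome. If the true rates differ between arms, power can lie well above or below either set of figures.

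This corrects stated figures. It does not show that 150 per group is the wrong number, and it leaves the test, alpha and inference untouched.

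**What to change.** - Re-run the Section 7.7 simulation with each patient's missingness drawn at random, and restate Table 7.7:2 as about 88%, 84% and 81%. The present values can stay beside them if labelled as assuming equal missing counts per arm.
- Reword the two sentences after the table: 150 per group gives about 88% power at 5% drop-out and about 81% at 10%, assuming independent drop-out at the same rate in both arms and unrelated to outcome; 90% power holds to about 3.5–4% missing.
- Preferably add one or two scenarios with unequal rates, since power is sensitive to them.
- Re-run Tables 7.7.1:2 and 7.7.1:4 in the same way. At alpha 5%, KCCQ at SD 13 and 15 and CHQ at SD 1.2 and 1.4 fall by about 1–2 points, CHQ at SD 1 falls by under 1 point, KCCQ at SD 17 is unchanged, and KCCQ at SD 20 rises by under 1 point.

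The cost is a re-run of existing simulations, the restated tables, two sentences and one stated assumption. The quoted power becomes slightly less favourable. No change in enrolment is needed.

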### 7.7.1 Power estimation for key secondary endpoints

#### KCCQ

For power estimation of the KCCQ-TSS a treatment difference of 5 points is assumed. In patients with heart failure previous studies have reported a standard deviation of the KCCQ TSS between 13 in the CONFIRM-HF trial and 19-21 in the FAIR-HF trial [[R17-1226](#), [R17-3097](#)].

Using a normal distribution to calculate the probability that an observation X in Empagliflozin group will be less than an observation Y in the control group under the alternative, a sample size of 150 per treatment group will result in approximately 55% to 90% power to detect a 5 point difference between treatment groups at an alpha-level of 5% using a Wilcoxon test, if all questionnaires are available at the end of the trial ([see Table 7.7.1: 1](#)).

Due to the Hochberg procedure, if CHQ dyspnea is not significant, an alpha-level of 2.5% will become applicable. [Table 7.7.1:1](#) therefore additionally shows an alpha-level of 2.5 %.

Table 7.7.1: 1 – Power Estimation for KCCQ-TSS

SD	P(X<Y)	Power for $\alpha = 5\%$	Power for $\alpha = 2.5\%$
13	0.393	89%	83%
15	0.407	79%	71%
17	0.418	69%	59%
20	0.430	55%	44%

While every effort will be made to collect the questionnaire for randomized patients regardless of being on or off treatment, about 5% missing questionnaires may be assumed and are considered for power evaluation in analogy with the primary endpoint.

Results of a simulation of the power with 100000 iterations to detect a 5 point difference between treatment groups in a Wilcoxon test with imputation rules analogously to the primary endpoint, assuming 5% missing questionnaires at week 12 in each treatment arm, a normal distribution for non-missing scores, and alpha of 5% is summarized in the [Table 7.7.1: 2](#) below.

Table 7.7.1: 2 – Simulation of Imputation Rules for KCCQ-TSS

SD	Power for $\alpha = 5\%$	Power for $\alpha = 2.5\%$
13	85%	76%
15	73%	61%
17	61%	49%
20	47%	35%

Overall power is reasonable to evaluate superiority of empagliflozin versus placebo assuming a treatment effect of 5 points and a standard deviation that does not exceed 15 points.

### CHQ

For power estimation of the CHQ dyspnea a treatment difference of 0.5 points is assumed [[R99-1220](#)]. CHQ and CRQ (an instrument almost identical to CHQ used in respiratory disease) are reported as performing similarly [[R99-1220](#)]. A standard deviation of the change

from baseline of the standardized CRQ dyspnea score of 1.15 has been reported [[R05-1404](#)]. Similar data were also reported for CHQ [[R17-2917](#)]. Therefore, for power estimation, a standard deviation of 1 to 1.4 is assumed.

Using a normal distribution to calculate the probability that an observation X in Empagliflozin group will be less than an observation Y in the control group under the alternative, a sample size of 150 per treatment group will result in approximately 84% to 98% power per score to detect a 0.5 point difference between treatment groups at an alpha-level of 5% using a Wilcoxon test, if all questionnaires are available at the end of the trial (see [Table 7.7.1:3](#)).

Due to the Hochberg procedure, if KCCQ-TSS is not significant, an alpha-level of 2.5% will become applicable. [Table 7.7.1: 3](#) therefore additionally shows an alpha-level of 2.5 %.

Table 7.7.1: 3 – Power Estimation for CHQ-SAS

SD	P(X<Y)	Power for $\alpha = 5\%$	Power for $\alpha = 2.5\%$
1	0.362	98%	97%
1.2	0.384	93%	89%
1.4	0.400	84%	77%

While every effort will be made to collect the questionnaire for randomized patients regardless of being on or off treatment, about 5% missing questionnaires may be assumed and are considered for power evaluation in analogy with the primary endpoint.

Results of a simulation of the power with 100000 iterations to detect a 0.5 point difference between treatment groups in a Wilcoxon test with above imputation rules, assuming 5% missing questionnaires at week 12 in each treatment arm, a normal distribution for non-missing scores, alpha of 5% is summarized in the [Table 7.7.1:4](#) below.

Table 7.7.1: 4 – Simulation of Imputation Rules for CHQ-SAS

SD	Power for $\alpha = 5\%$	Power for $\alpha = 2.5\%$
1	98%	95%
1.2	90%	83%
1.4	79%	69%

Overall a power of approximately 70% or higher is expected to detect a difference of 0.5 for each score given the planned sample size of 150 patients per treatment group.

Calculations were performed using nQuery Advisor® 7.0 statistical package by Statistical Solutions Ltd and simulation was performed using R version 3.3.2 by The R Foundation for Statistical Computing.

## **8. INFORMED CONSENT, TRIAL RECORDS, DATA PROTECTION, PUBLICATION POLICY, AND ADMINISTRATIVE STRUCTURE**

The trial will be carried out in accordance with the Medical Devices Directive (93/42/EEC) and the harmonised standards for Medical Devices (ISO 14155, current version).

The trial will be carried out in compliance with the protocol, the ethical principles laid down in the Declaration of Helsinki, in accordance with the ICH Harmonized Tripartite Guideline for Good Clinical Practice (GCP), relevant BI Standard Operating Procedures (SOPs), the EU regulation 536/2014 and other relevant regulations.

Standard medical care (prophylactic, diagnostic and therapeutic procedures) remains the responsibility of the treating physician of the patient.

The investigator will inform the sponsor immediately of any urgent safety measures taken to protect the trial patients against any immediate hazard, as well as of any serious breaches of the protocol or of ICH GCP.

The Boehringer Ingelheim transparency and publication policy can be found on the following web page: [trials.boehringer-ingelheim.com](http://trials.boehringer-ingelheim.com). The rights of the investigator and of the sponsor with regard to publication of the results of this trial are described in the investigator contract. As a rule, no trial results should be published prior to finalization of the Clinical Trial Report. The certificate of insurance cover is made available to the investigator and the patients, and is stored in the ISF.

### **8.1 TRIAL APPROVAL, PATIENT INFORMATION, INFORMED CONSENT**

This trial will be initiated only after all required legal documentation has been reviewed and approved by the respective Institutional Review Board (IRB) / Independent Ethics Committee (IEC) and competent authority (CA) according to national and international regulations. The same applies for the implementation of changes introduced by amendments.

Prior to patient participation in the trial, written informed consent must be obtained from each patient (or the patient's legally accepted representative) according to ICH / GCP and to the regulatory and legal requirements of the participating country. Each signature must be personally dated by each signatory and the informed consent and any additional patient-information form retained by the investigator as part of the trial records. A signed copy of the informed consent and any additional patient information must be given to each patient or the patient's legally accepted representative."

The patient must be given sufficient time to consider participation in the trial. The investigator obtains written consent of the patient's own free will with the informed consent

form after confirming that the patient understands the contents. The investigator (or delegate) must sign (or place a seal on) and date the informed consent form. If a trial collaborator has given a supplementary explanation, the trial collaborator also signs (or places a seal on) and dates the informed consent.

Re-consenting may become necessary when new relevant information becomes available and should be conducted according to the sponsor's instructions.

The consent and re-consenting process should be properly documented in the source documentation.

